Circulating tumor DNA and saved sample for exploratory biomarkers	Blood	Cycle 1 Day 1, Cycle 2 Day 1, Every 3 cycles from Cycle 3 ^a , Upon discontinuation (+7 days) of CORT125281, Disease progression ^b	Detect aberrations that may be associated with therapeutic resistance including AR amplification
Spot urine (cortisol and creatinine) ^e	Urine	Cycle 1 Day 1, Cycle 2 Day 1, Every 3 cycles from Cycle 3 ^a , Upon discontinuation (+7 days) of CORT125281, Disease progression ^b	Cortisol and creatinine analysis by mass spectrometry by central laboratory. Assessments may include related analytes such as THS
24-hour UFC (cortisol and creatinine) ^e	Urine	Screening, Cycle 1 Day 22	UFC with creatinine will be measured by tandem mass spectrometry by central laboratory. Assessments may include related analytes such as THS

ACTH, adrenocorticotrophic hormone; AR, androgen receptor; ARV7, androgen-receptor splice variant 7 messenger RNA; CTC, circulating tumor cell; DHEA-S, dehydroepiandrosterone-sulfate; DNA, deoxyribonucleic acid; EOT, End-of-Treatment; GC, glucocorticoid; GR, glucocorticoid receptor; IHC, immunohistochemistry; mRNA, messenger RNA; THS, tetrahydrodeoxycortisol; UFC, urinary free cortisol.

^a. After 1 year, the sampling frequency will decrease to every 6 months.

^b. If patients discontinue CORT125281 for reasons other than disease progression, the sample will be collected upon disease progression.

- ^c. Both pre-dose (fasted) and 4 hr post-dose (not fasted).
- ^d. Paired biopsies collected with the first biopsy obtained within 6 weeks prior to initiating CORT125281/enzalutamide. Soft tissue biopsy is preferred, when possible. Optional: consent to provide additional on-study biopsy (1) obtained during procedure conducted as standard of care; or (2) at the time of disease progression.
- ^e. Spot urine test will be conducted during the scheduled visit. The 24-hour UFC sample will be collected at home the day prior to the visit. The Screening 24-hour UFC sample can be collected anytime between Screening and the first dose of CORT125281.

Table 20 Pharmacokinetic Schedule of Assessments, Dose-Determination Phase Segment 1

PK Sample	Day	Nominal Time	Window
Enzalutamide	Cycle 1 Day -1 (Lead-in)	0 hour, pre-dose	Within 15 minutes before the morning dose of enzalutamide
		30 minutes	Within 5 minutes of nominal time
		1 hour	
		1.5 hours	
		2 hours	±10 minutes
		3 hours	
		4 hours	
		6 hours	
		8 hours	
		12 hours	±30 minutes
		24 hours ^a , pre-dose	
CORT125281 & Enzalutamide	Cycle 1 Day 1	0 hour, pre-dose	Within 15 minutes before the morning dose of study treatment
		30 minutes	Within 5 minutes of nominal time
		1 hour	
		1.5 hours	
		2 hours	±10 minutes
		3 hours	
		4 hours	
		6 hours	
		8 hours	
		12 hours	±30 minutes
		24 hours ^a , pre-dose	

PK Sample	Day	Nominal Time	Window
CORT125281 & Enzalutamide	Cycle 1 Day 22	0 hour, pre-dose	Within 15 minutes before the morning dose of study treatment
		2 hours	±10 minutes
CORT125281 & Enzalutamide	Cycle 2 Day 1	0 hour, pre-dose	Within 15 minutes before the morning dose of study treatment
		30 minutes	Within 5 minutes of nominal time
		1 hour	
		1.5 hours	
		2 hours	±10 minutes
		3 hours	
		4 hours	
		6 hours	
		8 hours	
		12 hours	±30 minutes
CORT125281 & Enzalutamide	Cycle 2 Day 15	0 hour, pre-dose	Within 15 minutes before the morning dose of study treatment
		2 hours	±10 minutes
CORT125281 & Enzalutamide	Cycle 3 Day 1	0 hour, pre-dose	Within 15 minutes before the morning dose of study treatment
		2 hours	±10 minutes
CORT125281 ^b	Intra-patient dose escalation: On current dose and 4 weeks following dose adjustment	0 hour, pre-dose	Within 15 minutes before the morning dose of CORT125281
		2 hours	±10 minutes
Enzalutamide ^b	Intra-patient dose escalation: On current dose and 4 weeks following dose adjustment	0 hour, pre-dose	Within 15 minutes before the morning dose of enzalutamide
		2 hours	±10 minutes

Note: On all days with pharmacokinetic assessments, CORT125281 and enzalutamide should be taken at the same time in the clinic. Both the times of the previous day's doses of CORT125281 and enzalutamide and the times of the current day's doses should be recorded.

^a. The Cycle 1 Day -1 24-hour enzalutamide sample and the Cycle 1 Day 1 pre-dose sample may be a single sample, if the timepoints align.

The Cycle 1 Day 1 24-hour sample should be taken prior to dosing on Cycle 1 Day 2.

^b. Patients who undergo intra-patient dose escalation of CORT125281.

Table 21 Pharmacokinetic Schedule of Assessments – Dose-Determination Phase Segment 2

PK Sample	Day	Nominal Time ^a	Window
CORT125281 & Enzalutamide	Cycle 1 Day 15	0 hour, pre-dose	Within 15 minutes before the dose of study treatment
		1 hour	±10 minutes
		2 hours	
		3 hours	
		4 hours	
		6 hours ^b	
CORT125281 & Enzalutamide	2 weeks (±2 days) after each dose escalation ^c	0 hour, pre-dose	Within 15 minutes before the dose of study treatment
		1 hours	±10 minutes
		2 hours	
		3 hours	
		4 hours	
		6 hours ^b	
CORT125281 ^d	After a patient dose reduces and maintains dose for 2 weeks (±2 days) ^d	0 hour, pre-dose	Within 15 minutes before the dose of study treatment
		1 hour	±10 minutes
		2 hours	
		3 hours	
		4 hours	

PK, pharmacokinetic.

Note: On all days with PK assessments, CORT125281 and enzalutamide should be taken at the same time in the clinic. Both the times of the previous day's doses of CORT125281 and enzalutamide and the times of the current day's doses should be recorded.

^a. Nominal times are relative to the dose of study treatment (both CORT125281 and enzalutamide).

^b. The 6-hour PK timepoint may be omitted based upon available PK data.

^c. Must be collected after maintaining the CORT125281 dose for 14 days and prior to any dose modification.

^d. This sample only applies to those patients who require a dose reduction of CORT125281 (see Section 5.7.1) and must be collected prior to further dose modification.

Table 22 Pharmacokinetic Schedule of Assessments, Expansion Phase

PK Sample	Day	Nominal Time	Window
Both Expansion Cohorts			
CORT125281 & Enzalutamide	Cycle 2 Day 1	0 hour, pre-dose	Within 15 minutes before the morning dose of study treatment
		2 hours	±10 minutes
CORT125281 & Enzalutamide	Cycle 3 Day 1	0 hour, pre-dose	Within 15 minutes before the morning dose of study treatment
		2 hours	±10 minutes
Abi-Resistant Cohort Food-Effect Subcohort Only ^a			
CORT125281	Cycle 1 Day -7	0 hour, pre-dose	Within 15 minutes before the morning dose of study treatment
		30 minutes	Within 5 minutes of nominal time
		1 hour	
		1.5 hours	
		2 hours	±10 minutes
		3 hours	
		4 hours	
		6 hours	
		8 hours	
		12 hours ^b	±30 minutes
		24 hours	

PK Sample	Day	Nominal Time	Window
CORT125281	Cycle 1 Day 1	0 hour, pre-dose	Within 15 minutes before the morning dose of study treatment
		30 minutes	Within 5 minutes of nominal time
		1 hour	
		1.5 hours	
		2 hours	±10 minutes
		3 hours	
		4 hours	
		6 hours	
		8 hours	
		12 hours ^b	±30 minutes
		24 hours, pre-dose	

PK, pharmacokinetic.

Note: On all days with PK assessments, CORT125281 and enzalutamide should be taken at the same time in the clinic. Both the times of the previous day's doses of CORT125281 and enzalutamide and the times of the current day's doses should be recorded.

^a. Only for 10 patients enrolled in the Abi-Resistant Cohort.

^b. The 12-hour PK timepoint may be omitted based upon available PK data.

^c. The Cycle 1 Day 1 24-hour sample should be taken prior to dosing on Cycle 1 Day 2.

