^a. The DRC will review the safety, PK, and PD data from Dose-Determination Phase Segment 1 once a minimum of 3 evaluable patients have completed the DLT-evaluation period (Section 5.4.1).

^b. Enzalutamide will be at the dose currently tolerated by the patient at the time of Screening.

^c. The investigational agent will be increased in 40-mg increments every 2 weeks, as tolerated, with CORT125281 to a maximum dose of 320 mg QD under fed conditions (Arm A) or with placebo (Arm B) to maintain a CORT125281 dose of 240 mg QD under fed conditions (Table 8).

^d. After the DRC meeting for Dose-Determination Segment 2, patients initially randomized to Arm B will have their CORT125281 dose escalated per the recommended Phase 2 regimen.

Patients will participate in the following study periods:

- **Screening Period** will take place within 28 days before the first dose of study treatment
- **Lead-In Period:**
 - Dose-Determination Phase Segment 1: Enzalutamide monotherapy for 28 days
 - Dose-Determination Phase Segment 2: No Lead-In Period
 - Expansion Phase:
 - Food-Effect Subcohort: A single dose of CORT125281 under fasting conditions on Cycle 1 Day -7, and a single dose of CORT125281 30 minutes after a standard breakfast on Cycle 1 Day 1
 - Non-Food-Effect Patients: No Lead-In Period
- **Combination Treatment Period:** Patients will take combination treatment (CORT125281 and enzalutamide) until reaching disease progression, experiencing unmanageable toxicity, or until other treatment discontinuation criteria are met. Patients will continue assessments per the Schedule of Assessments (SoA) for the Combination Treatment Period until both CORT125281 and enzalutamide are discontinued.
- **Follow-Up Period:** Patients will return for a Post-Treatment Follow-Up Visit (End-of-Treatment [EOT] +30 Days Visit) 30 days after their final dose of CORT125281 or enzalutamide, whichever is later. After this, patients will continue to be followed for progression, information on subsequent anticancer therapies (start and end date and response), and survival.

PK, PD, safety, PRO and QoL evaluations will be performed throughout along with preliminary evaluations of antitumor activity as shown in the SoAs ([Appendix A](#)).

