7.3 Combination Treatment Period

Cycle 1 will begin the day after Screening is complete for patients in Dose-Determination Phase Segment 2 and the following patients in the Expansion Phase:

- Patients in the Abi-Resistant Cohort who are NOT in the Food-Effect Subcohort
- All patients in the ARant-Resistant Cohort

Cycle 1 will begin the day after the Lead-In Period is complete for all patients in Dose-Determination Phase Segment 1 and patients in the Expansion Phase Food-Effect Subcohort.

The acceptable visit window is ± 1 day for all visits during Cycle 1, unless the window spans a weekend; and ± 3 days for all other cycles. Visit windows are relative to Cycle 1 Day 1.

Study-related activities to be performed at the in-clinic visits are described in [Appendix A](#).

The following assessments should be performed during each in-clinic visit during the Combination Treatment Period:

- Record concomitant medications
- Record AEs
- Physical examination
- Vital signs
- ECOG performance status
- Local laboratory tests (see [Table 11](#) for details)
 - CBC with differential
 - Chemistry, including LDH
- Review diary card

The following assessments should be performed on Day 1 of each cycle:

- Measure body weight
- Triplicate 12-lead ECG (Day 1 of Cycle 1 and Cycle 3 only, and Day 15 of Cycle 1)
- Local laboratory tests (see [Table 11](#) for details)
 - PT, aPTT, and INR (Day 1 of Cycles 1 through 3)
 - Urinalysis (Day 1 of Cycles 1 through 3 and every third cycle after Cycle 3)
 - TSH, with reflex FT4 and TT3 or FT3 (every 3 months for the first year, starting with Day 1 of Cycle 3, and then every 6 months after the first year)
 - PSA
 - Serum amylase and lipase (each study visit through completion of Cycle 3, then every 3 months until completion of 12 months of study treatment)
- Dispense study treatment
- Provide patient diary card
- Study treatment accountability

Following the baseline/pre-treatment assessment, radiographic tumor assessments should be performed 8 weeks from the first dose of study treatment (CORT125281 or on-study enzalutamide, whichever is earlier), and then every 8 weeks for the first 24 weeks and every 12 weeks thereafter. For on-study scans, a window of ± 14 days is acceptable with the timing of the scans based on Cycle 1 Day 1.

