APPENDIX A: SCHEDULE(S) OF ASSESSMENTS

Table 16 Overall Schedule of Assessments

Study Period	Screening	Lead-In Period ^a	Combination Treatment Period (28-Day Cycles) ^b								End of Treatment	Post-Treatment Follow-Up ^c	
Cycle	Screening	Cycle 1	Cycle 1	Cycle 1	Cycle 1	Cycle 2	Cycle 2	Cycle 3	Cycle 4 & Beyond ^b	Every 3 Cycles from Cycle 3	EOT	EOT +30 Days	Every 4 Mnth
Day		Day -28 or Day -7	Day 1	Day 8	Days 15 & 22	Day 1	Day 15	Day 1	Day 1	Day 1			
Visit Window			± 1 Day	± 1 Day	± 1 Day	± 3 Days	± 3 Days	± 3 Days	± 3 Days	± 3 Days			± 10 Days
Written informed consent	X												
Tumor biopsy	X ^d					X ^d							
Review inclusion/exclusion criteria	X	X ^e	X ^e										
Record medical and oncology history	X	X ^e	X ^e										
Record prior medications	X	X ^e	X ^e										
Record concomitant medications		X	X ^f	X	X	X	X	X	X		X	X	X
Record adverse events	X	X	X ^f	X	X	X	X	X	X		X	X	
Physical examination ^g	X	X	X ^f	X	X	X	X	X	X		X	X	
Measure height	X												
Measure body weight	X	X	X			X		X	X		X	X	
Vital signs	X	X	X	X	X	X	X	X	X		X	X	
ECOG performance status	X	X	X ^f	X	X	X	X	X	X		X	X	
12-lead ECG (triplicate)	X		X ^h		X ^h			X ^h				X	
CBC with differential ⁱ	X ^j		X ^f	X	X	X	X	X	X		X	X	
Chemistry, including LDH	X ^j		X ^f	X	X	X	X	X	X		X	X	
Serum amylase and lipase	X		X	X	X	X	X	X		X ^k			

Study Period	Screening	Lead-In Period ^a	Combination Treatment Period (28-Day Cycles) ^b								End of Treatment	Post-Treatment Follow-Up ^c	
Cycle	Screening	Cycle 1	Cycle 1	Cycle 1	Cycle 1	Cycle 2	Cycle 2	Cycle 3	Cycle 4 & Beyond ^b	Every 3 Cycles from Cycle 3	EOT	EOT +30 Days	Every 4 Mnth
Day		Day -28 or Day -7	Day 1	Day 8	Days 15 & 22	Day 1	Day 15	Day 1	Day 1	Day 1			
Visit Window			± 1 Day	± 1 Day	± 1 Day	± 3 Days	± 3 Days	± 3 Days	± 3 Days	± 3 Days			± 10 Days
PT, aPTT, and INR	X ^j		X ^f			X		X			X		
Urinalysis	X ^j		X ^f			X		X		X	X	X	
TSH, with reflex FT4 and TT3/FT3	X ^j							X ^l					
Hepatitis B and C serologies and HIV	X												
Pharmacodynamic sampling ^m													
Whole blood sample pharmacogenomics testing (Dose-Determination Segment 1 only)	X												
Pharmacokinetic blood samples ⁿ													
Radiographic tumor assessment: CT/MRI, and bone scan ^{o,p}	X ^o					X			X		X		
Tumor markers: PSA	X		X			X		X	X		X		
PRO and QoL assessments ^q		X	X					X		X		X	X
Dispense study treatment ^r		X	X			X		X	X				
Provide diary card		X	X			X		X	X				
Study treatment accountability			X			X		X	X		X		
Survival follow-up													X ^s

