aPTT, activated partial thromboplastin time; CBC, complete blood count; CT, computed tomography; DRC, Data Review Committee; ECG, electrocardiogram; ECOG, Eastern Cooperative Oncology Group; EOT, End-of-Treatment; FACT-P, Functional Assessment of Cancer Therapy-Prostate; FT3, free triiodothyronine; FT4, free thyroxine; INR, international normalized ratio; LDH, lactic dehydrogenase; Mnth, month; MRI, magnetic resonance imaging; PSA, prostate-specific antigen; PRO, patient-reported outcomes; PT, prothrombin time; QoL, quality of life; TSH, thyroid-stimulating hormone; TT3, total triiodothyronine.

Note: In all parts of the study, a cycle of therapy is considered to be 28 days with no rest periods in between cycles. All procedures within a cycle should be counted by calendar day from Day 1 of that cycle. A 2-day window will be allowed for study visits.

- a. The Lead-In Period only applies to patients in Dose-Determination Phase Segment 1 and patients in the Expansion Phase Food-Effect Subcohort. Lead-in duration is 28 days in Dose-Determination Phase Segment 1, and 7 days for patients in the Expansion Phase Food-Effect Subcohort. When a recommended dose of enzalutamide is determined by the DRC, the DRC may recommend discontinuing the lead-in for subsequent cohorts.
- b. Upon discontinuation of CORT125281, if the patient continues on enzalutamide alone (Section 5.7.1.1) and all toxicities attributed to CORT125281 have resolved, visit frequency can be decreased per the Investigator's standard of care. The patient should come for their regularly scheduled visit (the subsequent cycle) after discontinuing CORT125281. After this visit, visits can be conducted less frequently per Investigator discretion, but at a minimum every 3 cycles while on enzalutamide alone; at these visits they will have the assessments listed in the "Cycle 4 & Beyond" column. After discontinuation of enzalutamide, the patient will return for their EOT Visit, and then for an EOT +30 Days Visit.
- c. Phone follow-up for overall survival (ie, the date and cause of death, and post-treatment information) will continue every 4 months until the study endpoints are met or 2 years from the date that the last patient enrolls in the study (whichever is later).

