- l. Every 3 months for the first year starting with Cycle 3 Day 1 and after 1 year the frequency will decrease to once every 6 months.
- m. Refer to [Table 17](#) (Dose-Determination Phase Segment 1), [Table 18](#) (Dose-Determination Phase Segment 2), and [Table 19](#) (Expansion Phase) for detailed pharmacodynamic sample schedules.
- n. Refer to [Table 20](#) (Dose-Determination Phase Segment 1), [Table 21](#) (Dose-Determination Phase Segment 2), and [Table 22](#) (Expansion Phase) for detailed pharmacokinetic sample schedules.

- ^o. Isolated new lesions on bone scan at <12 weeks from Cycle 1 Day 1 will be confirmed with a repeat bone scan at 6 weeks to rule out bone scan flare: refer to Prostate Cancer Clinical Trials Working Group 3 for 2+2 rule.
- ^p. Tumor assessments (CT/MRI, bone scan): The baseline tumor assessment should be performed within 28 days prior to the first dose of enzalutamide (for Dose-Determination Phase Segment 1) and/or CORT125281 (for Dose-Determination Phase Segment 2 and the Expansion Phase). The first on-study tumor assessment should be performed 8 weeks from the first dose of study treatment (CORT125281 or on-study enzalutamide, whichever is earlier) and then every 8 weeks for the first 24 weeks and every 12 weeks thereafter, at the EOT Visit (if not performed within 4 weeks), and as clinically indicated. For on-study scans, a window of ± 14 days is acceptable with the timing of the scans based on Cycle 1 Day 1.
- ^q. Includes FACT-P and questions relating to patient-reported pain. To be performed prior to dose during the following visits: Prior to initiation of CORT125281 and/or enzalutamide, at the completion of the Lead-In Period (applicable to patients in Dose-Determination Phase Segment 1 and patients in the Expansion Phase for whom food-effect will be assessed), Cycle 3 Day 1, every 3 cycles after Cycle 3 Day 1, and at the End-of-Treatment +30 Days Visit. For patients who discontinue treatment prior to disease progression, the questionnaires will be performed per the Schedule of Assessments until unequivocal progressive disease is documented.

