8.11. Interim Analyses or Timing of Analyses

The DRC consisting of Investigators, the Medical Monitor, a Clinical Pharmacologist, and additional members as appropriate will review the safety, PK, and PD data following the

completion of each cohort during Dose-Determination Phase Segment 1, after all patients have completed 3 cycles of treatment in Dose-Determination Phase Segment 2, and at least every 6 months during the Expansion Phase.

An interim safety analysis will be conducted after a total of 20 patients complete 3 cycles of therapy in the Expansion Phase. If at any time during the Expansion Phase the DLT rate exceeds 33%, the dose will be declared non-feasible, and no additional patients will be enrolled to that dose. A lower dose level may be evaluated, per the recommendation of the DRC.

9. Efficacy Analyses

The recommendations of the PCWG3 will be used to determine disease response for this study. Tumor assessments include ^{99m}Tc -methylene diphosphonate radionucleotide bone scintigraphy and CT of the chest, abdomen, and pelvis. Baseline tumor assessment will be performed within 28 days before the first dose of enzalutamide (for Dose-Determination Phase Segment 1) and/or the first dose of exicorilant (for Dose-Determination Phase Segment 2 and Expansion Phase). Post-baseline tumor assessments will be performed every 8 weeks after the first dose of enzalutamide and/or exicorilant for the first 24 weeks. Thereafter, tumor assessments will occur at intervals of 12 weeks until disease progression. Objective responses will be confirmed no less than 4 weeks after the criteria for response are first met (if possible, 4 – 6 weeks). PSA, alkaline phosphatase (ALP), and lactic dehydrogenase (LDH) will be assessed at the Baseline/Screening Visit and Day 1 of each cycle. The ITT population will be used to address the secondary and exploratory efficacy objectives of the study. Disease response and progression assessed according to RECIST v1.1 by the Investigator will provide the basis for efficacy endpoints.

At all scheduled visits, data recorded for target, non-target, and new lesions, and Investigator response assessment will be presented in by-patient listings. Summary tables and figures will be provided for endpoints as described in the following sections. Response rate endpoints will be summarized by providing the point and interval estimates. Time-to-event variables will be summarized using Kaplan-Meier estimates and plots.

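### The Table 16 scan grid contradicts its own footnote and the 8-week text for every group without the 28-day enzalutamide lead-in

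*Protocol*

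**What the plan says.** The Table 16 row "Radiographic tumor assessment: CT/MRI, and bone scan" has marks under Screening, Cycle 2 Day 1, Cycle 4 & Beyond, and End of Treatment. Cycle 2 Day 15, Cycle 3 Day 1 and the column for every third cycle from Cycle 3 are blank.

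Footnote p, attached to that row, says: "The first on-study tumor assessment should be performed 8 weeks from the first dose of study treatment (CORT125281 or on-study enzalutamide, whichever is earlier". It continues with 8-week scans to week 24 and 12-week scans after that. It allows 14 days either side, "with the timing of the scans based on Cycle 1 Day 1". Protocol 6.7 and 7.3 repeat the interval, the window and both reference points; in 7.3, "radiographic tumor assessments should be performed 8 weeks from the first dose of study treatment". Protocol 3.1 gives the same interval. SAP Section 9 says: "Post-baseline tumor assessments will be performed every 8 weeks after the first dose of enzalutamide and/or exicorilant for the first 24 weeks".

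On the calendar, Table 16 states that "a cycle of therapy is considered to be 28 days with no rest periods in between cycles" and that "Lead-in duration is 28 days in Dose-Determination Phase Segment 1, and 7 days for patients in the Expansion Phase Food-Effect Subcohort". For Segment 2, Protocol 3.1 says "Dose-Determination Phase Segment 2: No Lead-In Period", and it says the same of Expansion patients outside the food-effect subcohort. SAP 8.8 records that Segment 1 Cohort 3 also had no lead-in.

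**The concern.** Table 16 is the overall schedule for all parts of the study. Protocol Section 6 makes adherence to the schedule of assessments mandatory, and Sections 5.7.1.1 and 7.3.1 send sites to Table 16 for continued scanning. The grid is therefore an operating instruction. If its marks fit only one lead-in group, a site that builds its visit calendar from the grid will image on different weeks from a site that works from the footnote.

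The endpoints exposed are rPFS and the progression-free proportions at 4, 6 and 12 months. Radiographic progression can be found only when a scan is done. SAP Table 3 also censors rPFS after two or more consecutive missed scheduled assessments, and that rule cannot be applied uniformly unless there is one schedule to count against.

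**Working it through.** **1. Column placement.** The table was read from PDF, so this was checked first. The scan row has 14 cells, the same number as the header and the PSA and coagulation rows. The PSA row is marked at both Cycle 2 Day 1 and Cycle 3 Day 1; the scan row is marked only at the first of these. The blank at Cycle 3 Day 1 is not an extraction shift.

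**2. Target.** Eight weeks is 56 days. With 14 days either side, the first scan belongs between 42 and 70 days after the anchor.

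**3. Where the cycles fall.** With 28-day cycles and a lead-in of L days, Cycle k Day 1 is 28 × (k − 1) + L days after the first dose of study treatment.

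| Group | L | Cycle 2 Day 1 | Cycle 3 Day 1 | Within days 42–70 |
|---|---|---|---|---|
| 28-day lead-in | 28 | 28 + 28 = 56 (week 8) | 56 + 28 = 84 (week 12) | Cycle 2 only |
| Food-effect subcohort | 7 | 28 + 7 = 35 (week 5) | 56 + 7 = 63 (week 9) | Cycle 3 only |
| No lead-in | 0 | 28 (week 4) | 56 (week 8) | Cycle 3 only |

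The 3-day visit window does not rescue the Cycle 2 mark. It reaches day 31 with no lead-in and day 38 in the food-effect subcohort, both short of day 42.

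**4. Later scans.** Read literally, the mark under Cycle 4 & Beyond means a scan on Day 1 of every cycle from Cycle 4. With no lead-in that is weeks 12, 16, 20, 24, 28 and so on. The text requires weeks 16 and 24, then every 12 weeks. The grid and the text therefore disagree after the first scan as well.

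**5. Anchor.** First dose and Cycle 1 Day 1 differ by L days: 28 for the 28-day lead-in (more than the 14-day window), 7 for the food-effect subcohort (inside it), and 0 otherwise. Counted from Cycle 1 Day 1, Cycle 2 Day 1 is week 4 for everyone, and the grid fits no group.

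**6. Who is affected.** Segment 2 has about 20 patients. Expansion has about 40, of whom 10 are food-effect and 40 − 10 = 30 have no lead-in. The grid therefore fits none of these roughly 20 + 40 = 60 patients, nor Segment 1 Cohort 3 (seven enrolled, Protocol 1.3.2.1). It fits Cohorts 1 and 2, which had 2 + 3 = 5 patients treated with the combination.

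**The case against.** The strongest reply is that in Table 16 the footnotes carry the timing. Thyroid testing has a single on-treatment mark, at Cycle 3, and footnote l turns it into a repeating schedule. The ECG marks are likewise narrowed by footnote h. On that reading the scan row means what footnote p says, and no sentence in either document orders a week-4 scan. This stands in part. A reader might infer that Segment 2 and Expansion patients will be scanned at week 4; the documents do not support that. It happens only where a site follows the mark and passes over the footnote. But footnote h also shows that the table can confine a mark to Segment 1 when that is meant, and the Cycle 2 scan mark has no such limit. Footnote p itself has two anchors.

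A reader might also infer a shift of several percentage points in the 4- and 6-month progression-free proportions. That requires reading the later mark as every second cycle (weeks 4, 12, 20), which the grid does not say, together with an assumed rPFS median. Read literally, the grid includes scans at weeks 16 and 24. Using the SAP month of 30.4375 days, 4 months is 4 × 30.4375 / 7 = 17.4 weeks and 6 months is 26.1 weeks. The last scans before these landmarks then fall at weeks 16 and 24 under both the grid and the text, so no landmark gap follows.

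Nor does bone-scan flare separate the two calendars. Footnote o applies to new lesions before 12 weeks, which covers week 8 as well as week 4.

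Finally, DLT is the primary endpoint, Expansion is sized on PSA response, and SAP 7.3 uses actual scan dates, so an off-schedule scan is still dated correctly. These points limit the severity. They do not remove the contradiction.

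**Conclusion.** The Table 16 scan row is wrong as written for every group without the 28-day lead-in: Segment 2, all Expansion patients and Segment 1 Cohort 3. Its Cycle 2 Day 1 mark falls at week 4, or week 5 for the food-effect subcohort, against a stated 8 weeks with 14 days either side. The week-8 visit is blank. The later mark conflicts with the stated interval, and the double anchor matters only for 28-day lead-in patients.

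Severity is minor to moderate. rPFS is a secondary endpoint summarised descriptively, and the footnote on the row already gives the 8-week timing. No numerical bias is claimed: its size would depend on how many sites follow the grid and how they read the later mark, and the documents settle neither. The conclusion rests only on the cycle length, lead-in lengths and scan window stated in the protocol, and on the column reading checked above.

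**What to change.** Reconcile the Table 16 row with the 8-week text, by lead-in group:

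- **Without the 28-day lead-in:** move the mark from Cycle 2 Day 1 to Cycle 3 Day 1, show Cycles 5 and 7 Day 1 (weeks 16 and 24 with no lead-in), then every 12 weeks. In the food-effect subcohort these visits fall at weeks 9, 17 and 25 from first dose, inside the window.
- **With the 28-day lead-in:** keep Cycles 2, 4 and 6 Day 1 (weeks 8, 16 and 24 from first dose), then every 12 weeks.
- **Cycle 4 & Beyond:** replace the open mark with the named cycles.
- **Anchor:** state it once in footnote p, 6.7 and 7.3 as the first dose of study treatment, which is where the rPFS clock starts in Protocol 9.5.5 and SAP 9.1. Remove the Cycle 1 Day 1 reference.

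The cost is one table row and one repeated sentence, in the next amendment or a memo to sites. It adds no scans beyond those the text already requires. It also gives the SAP Table 3 missed-assessment rule a single schedule to count against.
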